3.1.2.2. Sub-Study B

- OR is defined as complete response (CR) or partial response (PR) according to RECIST v1.1 from the date of first study treatment until the date of the first documentation of progressive disease (PD). Both CR and PR must be confirmed by repeat assessments performed no less than 4 weeks after the criteria for response are first met.

3.2. Secondary Endpoints

3.2.1. Safety endpoints

- AEs graded according to the NCI-CTCAE v5.0 and changes in clinical laboratory parameters.

AEs will be graded by the investigator according to the Common Terminology Criteria for Adverse Events (CTCAE) version 5.0 and coded using the Medical Dictionary for Regulatory Activities (MedDRA)

3.2.2. Efficacy endpoints

3.2.2.1. Sub-Study A and Sub-Study B

Durable OR (for Phase 1b Sub-Study A only refer to Section 3.1.2.1), OR (Phase 1b and Phase 2), TTR (Phase 2), DR (Phase 2), and PFS (Phase 2) will be summarized based on investigator assessment using RECIST v1.1. OS will be summarized for Phase 2.

- OR is defined as complete response (CR) or partial response (PR) according to RECIST v1.1 from the date of first study treatment until the date of the first documentation of progressive disease (PD). Both CR and PR must be confirmed by repeat assessments performed no less than 4 weeks after the criteria for response are first met.

- TTR is defined for participants with OR, as the time from the date of first dose of study treatment to the date of first documentation of objective response (CR or PR) which is subsequently confirmed.
- DR is defined for participants with confirmed OR, as the time from the the date of first documentation of OR to the date of the first documentation of PD or to death due to any cause, whichever occurs first.
- PFS is defined as the time from the date of first dose of study treatment to the date of first documentation of PD or death due to any cause, whichever occurs first.
- OS is defined as the time from the date of first dose of study treatment to the date of death due to any cause.

3.2.3. Pharmacokinetic endpoints

- PK parameters of sasanlimab, encorafenib, binimetinib (Sub-Study A), sasanlimab, axitinib, SEA-TGT (Sub-Study B), and applicable metabolites, as data permit.
- PK parameters for sasanlimab include AUC, Cmax, Tmax and Ctough (Sub-Study A and B).
- PK parameters of interest for encorafenib, binimetinib (Sub-Study A only) include Ctough
- PK parameters of interest for axitinib (Sub-Study B only) include Cmax and Ctough
- PK parameters of interest for SEA-TGT (Sub-Study B only) include AUC, Cmax, and Ctough.

Table 3. Definitions for PK Parameters to be Determined as Data Permit

Parameter	Definition	Method of Determination
AUC _{sd,τ} AUC _{ss,τ}	Area under the plasma concentration-time profile from time zero to the next dose (after single dose and at steady state)	Linear/Log trapezoidal method
Cmax	Maximum observed plasma concentration	Observed directly from data
Tmax	Time for Cmax	Observed directly from data as time of first occurrence
t _{1/2a}	Terminal half-life	Log(2)/kel, where kel is the terminal phase rate constant calculated by a linear regression of the log-linear concentration-time curve. Only those data points judged to describe the terminal log-linear decline were used in the regression.
Ctough	Pre-dose concentration during multiple dosing	Observed directly from data

CL/Fa	Apparent clearance	Dose / AUC_{τ} for steady state
Vz/Fa	Apparent volume of distribution	Dose / ($AUC_{\tau} \cdot kel$) for steady state
$AUC_{sd,\tau}$ (dn) $AUC_{ss,\tau}$ (dn)	Dose normalized AUC	AUC / Dose
Cmax(dn)	Dose normalized Cmax	Cmax / Dose

3.2.4. Immunogenicity endpoints

- ADA and nAb (i.e., incidence) against sasanlimab (Sub-Study A), sasanlimab and SEA-TGT (Sub-Study B), as data permit

3.2.5. Biomarker endpoints

- PD-L1 expression in baseline tumor samples

Table 7. Biomarker Definition and Determination

Parameter	Definition	Method of Determination
PD-L1 expression	The percent of counted cells scored as PD-L1+ and qualitative assessment of PD-L1 staining on tumor and immune cells as defined by cell morphology in regions of interest	Pathologist, assisted by image analysis

3.2.6. Patient Reported Outcomes endpoints

- Health-related quality of life as measured by EORTC QLQ-C30/LC13

PROs endpoints (for Phase 2 Sub-Study A only) will be assessed using the European Organization for Research and Treatment of Cancer Quality of Life Questionnaire (EORTC QLQ-C30) and its corresponding module for lung cancer (EORTC QLQ-LC13)⁴.

The EORTC QLQ-C30 consists of 30 questions, which can be grouped into 5 functional scales (physical, role, cognitive, emotional, and social); a global health status/global quality of life scale; 3 symptom scales (fatigue, pain, nausea and vomiting); and 6 single items that assess additional symptoms (dyspnea, appetite loss, sleep disturbance, constipation, and diarrhea); and financial impact. All scales and single item measures range in score from 0 to 100. Higher scores on the global health status/quality of life scale represent higher health status/quality of life. Higher scores on the functional scales represent higher levels of functioning. Higher scores on the symptom scales/items represent a greater presence of symptoms.

The EORTC QLQ-LC13 is the lung cancer specific module of the EORTC Quality of Life Questionnaire. The EORTC QLQ-LC13 consists of 13 questions and includes 1 multi-item scale and 9 single items assessing symptoms (dyspnea, cough, haemoptysis, and site specific pain), side effects (sore mouth, dysphagia, peripheral neuropathy, and alopecia), and pain medication use. Similar to the EORTC QLQ-C30, higher scores are reflective of a greater presence of symptoms.

3.3. Exploratory Endpoints

3.3.1. Sub-study A and Sub-Study B

- Measurements of biomarkers, consisting of DNA, RNA, protein, metabolites or defined cell types, resulting from analyses of peripheral blood and/or tumor tissue biospecimen obtained at baseline, on treatment or at end-of-study.
- Depth of response by investigator assessment using RECIST v1.1 (Sub-Study A).

Depth of response is defined as a reduction in tumor burden (the sum of the diameters of target lesions). Depth of response will be summarized as a Deep Response, which is a confirmed response per RECIST v1.1 with a depth of response of at least 50%.

Participants who do not have a post-baseline tumor assessment due to early progression of disease, who receive anti-cancer therapies other than the study treatments prior to reaching a depth of response of at least 50% or who die, have PD, or stop tumor assessments for any reason prior to reaching a depth of response of $\geq 50\%$ will be counted as not having a Deep Response. Each participant will have a deep response status (0: depth of response $< 50\%$ OR; 1: depth of response $\geq 50\%$).

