6.2.2.1. Objective response as assessed by the Investigator per RECIST v1.1

Best overall response (BOR) will be assessed based on reported overall lesion responses at different evaluation time points from the date of first dose of study treatment until the first documentation of PD, according to the following rules. Only tumor assessments performed on or before the start date of any further anti-cancer therapies will be considered in the assessment of BOR. Clinical deterioration will not be considered as documentation of disease progression.

BOR Based on Confirmed Responses:

- CR = at least two determinations of CR at least 4 weeks apart and before first documentation of PD
- PR = at least two determinations of PR or better (PR followed by PR or PR followed by CR) at least 4 weeks apart and before first documentation of PD (and not qualifying for a CR)
- SD (applicable only to participants with measurable disease at baseline) = at least one SD assessment (or better) ≥ 6 weeks after the date of first dose of study treatment and before first documentation of PD (and not qualifying for CR or PR).
- Non-CR/non-PD (applicable only to participants with non-measurable disease at baseline) = at least one non-CR/non-PD assessment (or better) ≥ 6 weeks after the date of first dose of study treatment and before first documentation of PD (and not qualifying for CR or PR).
- PD = first documentation of PD ≤ 12 weeks after the date of first dose of study treatment (and not qualifying for CR, PR, SD or non-CR/non-PD).
- NE: all other cases.

An objective status of PR or SD cannot follow one of CR. SD can follow PR only in the rare case that tumor increases by less than 20% from the nadir, but enough that a previously documented 30% decrease from baseline no longer holds. If this occurs, the sequence PR-SD-PR is considered a confirmed PR. A sequence of PR – SD – SD – PD would be a best response of SD if the window for SD definition has been met.

Objective Response (OR) is defined as confirmed BOR of CR or PR according to RECIST v1.1.

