6.2.2.2. Tumor shrinkage from baseline

Tumor shrinkage will be summarized as the percent change from baseline in target lesions (sum of longest diameter for non-nodal lesion and short axis for nodal lesion) per time point.

It will be derived as:

- $((\text{Sum of target lesions at week XX} - \text{sum of target lesions at baseline}) / \text{sum of target lesions at baseline}) \times 100$

The maximum reduction in target lesions from baseline will be derived across all the post-baseline assessments until documented disease progression, excluding assessments after start of subsequent anti-cancer therapy, as:

- $\text{Minimum of } ((\text{sum of target lesions at week XX} - \text{sum of target lesions at baseline}) / \text{sum of target lesions at baseline}) \times 100$

A waterfall plot of maximum percent reduction in the sum of longest diameter for non-nodal lesions and short axis for nodal lesions from baseline will be created by treatment group.

These plots will display the best percentage change from baseline in the sum of the diameters of all target lesions for each participant with measurable disease at baseline and at least one post-baseline assessment.

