6.3. Other Endpoints

- Exploratory biomarker data will be analyzed based on the biomarker analysis sets as defined in Section 4 and as described in Section 6.2.5.

If data permits, appropriate descriptive statistics will be provided for the exploratory endpoints which will include DNA, RNA, and protein markers that may be relevant to the

- Depth of Response
- A Deep Response is defined as a confirmed response per RECIST v1.1 with a depth of response of at least 50%. The Deep response rate will be calculated along with the 2-sided 95% CI using the Clopper-Pearson method³ (exact CI for a binomial proportion as computed by default by the FREQ procedure using the EXACT option) by treatment group and based on the full analysis set.

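### Deep Response in Sub-Study A has no separate route for confirmed CR, so a complete responder with no target lesions, or with small nodal targets only, can be scored as not deep

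*SAP*

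**What the plan says.** Depth of response is an exploratory Phase 2 endpoint of Sub-Study A. SAP Section 3.3.1 states: "Depth of response is defined as a reduction in tumor burden (the sum of the diameters of target lesions". It summarises depth as a Deep Response, "which is a confirmed response per RECIST v1.1 with a depth of response of at least 50" percent. Section 6.3 repeats the rule: "A Deep Response is defined as a confirmed response per RECIST v1.1 with a depth of response of at least 50" percent, with the rate and its Clopper-Pearson interval computed "by treatment group and based on the full analysis set".

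The status is binary and assigned to all: "Each participant will have a deep response status", coded 1 for a depth of 50% or more and 0 for less. Participants who progress, die or "stop tumor assessments for any reason prior to reaching a depth of response of" 50% or more count as not deep.

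Three other sections bear on this:

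- Section 6.2.2.1 has a best-response category for participants without measurable disease: "Non-CR/non-PD (applicable only to participants with non-measurable disease at baseline". The CR rule in the same list is not limited to measurable disease, whereas the SD rule is.
- Section 6.5.1.3 tabulates measurable disease at baseline as yes or no.
- Section 6.2.2.2 builds the target sum as the "sum of longest diameter for non-nodal lesion and short axis for nodal lesion", and limits the waterfall plot to participants with measurable disease.

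**The concern.** A Deep Response rate is meant to pick out the participants whose tumours shrank most. Complete response is the best category in the SAP's own response list, yet the only way to score 1 is a percentage fall in the target-lesion sum. That percentage can fail to represent a CR in two ways: the sum may not exist, or it may stay above zero because a node that has returned to normal size still has a short axis. The rule could then score a confirmed CR as 0 and a confirmed PR with exactly 50% shrinkage as 1.

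The error runs in one direction only: it can remove complete responders from the numerator but never add anyone. A programmer who meets a confirmed CR with no target sum also has no stated instruction, and would have to choose after the data are in.

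**Working it through.** The SAP gives no expected rate or sample size for Deep Response, so there is no planned figure to reproduce. The check is of the rule itself.

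**Inputs.** From the SAP: depth is the reduction in the target-lesion sum, with a 50% threshold, 0/1 for everyone, FAS denominator (Sections 3.3.1 and 6.3); nodal short axis in the sum (6.2.2.2); about 62 participants in Phase 2 of Sub-Study A (2.2.1). Assumed, because the SAP invokes RECIST v1.1 without printing its nodal limits: a target node has a short axis of at least 15 mm, and nodal CR means below 10 mm.

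**Formula.** Percent reduction = 100 × (baseline sum − follow-up sum) / baseline sum.

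**Situation (a): no target lesions.** The baseline sum is absent, so the percentage is undefined and status 1 is unreachable. Code 0 (depth below 50%) is not literally true either, but one of the two codes is required. The rule on progressing, dying or stopping assessments before reaching 50% leads to 0.

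**Situation (b): nodal targets only.** For a single target node at CR:

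| Baseline (mm) | Follow-up 9.9 mm | 9 mm | 8 mm | 7 mm |
|---|---|---|---|---|
| 15 | 34.0% | 40.0% | 46.7% | 53.3% |
| 16 | 38.1% | 43.8% | 50.0% | 56.2% |
| 17 | 41.8% | 47.1% | 52.9% | 58.8% |
| 18 | 45.0% | 50.0% | 55.6% | 61.1% |
| 19 | 47.9% | 52.6% | 57.9% | 63.2% |
| 20 | 50.5% | 55.0% | 60.0% | 65.0% |

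For example, 16 to 9 mm gives (16 − 9)/16 = 43.8%. With two nodes, 15 and 15 mm each going to 9 mm gives (30 − 18)/30 = 40.0%; 18 and 16 mm each going to 9 mm gives (34 − 18)/34 = 47.1%. A single node of 20 mm or more always passes, because anything below 10 mm is more than a 50% reduction. The shortfall is therefore confined to nodes of 15 to just under 20 mm that shrink enough for CR but not to half their size.

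**Effect on the rate.** Each affected participant moves it by 1/62 = 1.6 points; two move it by 2/62 = 3.2 points. With an assumed count of 25 deep responders:

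- 25/62 = 40.3% (95% CI 28.1 to 53.6)
- one reclassified: 26/62 = 41.9% (29.5 to 55.2)
- two reclassified: 27/62 = 43.5% (31.0 to 56.7)

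**How many.** The SAP gives no CR rate. Suppose 5 to 10% have a confirmed CR (62 × 0.05 = 3.1; 62 × 0.10 = 6.2) and a third of these have nodal-only or non-measurable disease: 3.1/3 = 1.0 and 6.2/3 = 2.1, so 1 to 2 participants. This is a ceiling under those assumptions, since it counts every such CR as misclassified while the table shows that many nodal CRs pass.

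**The case against.** The strongest reply is that nothing is contradicted. Both sections give the same rule, the endpoint measures target-lesion shrinkage, and it is scored as defined. On that view the rate is too low only relative to a different endpoint in which any CR is deep. Confirmed CR is also tabulated separately under Section 6.2.2.1, so no complete response is hidden, and the primary durable response rate is untouched. These points stand, and they keep the matter small. They do not explain why a measure of the deepest responses should rank a 50% PR above a confirmed CR, or which code applies when no sum exists.

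Four stronger readings are tempting, and the document does not support them:

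- A reader might infer from Section 6.2.2.1 that participants with non-measurable disease are admitted. That section supplies a response category, not an eligibility rule. If the protocol requires measurable disease, situation (a) largely disappears; (b) does not.
- A reader might infer that the SAP expressly assigns 0 when there is no target sum. It has no rule for that case; 0 is implied.
- A reader might infer that nodal-only CRs generally fail. They fail only in the size window above, and only if no later assessment reaches 50%. The wording about reaching a depth suggests that any qualifying assessment may suffice.
- A reader might infer a downward bias of 1.6 to 3.2 points. The assumptions behind 1 to 2 participants have no support in the document, and zero is plausible.

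The contrast with the waterfall plot is not itself a defect. A plot of percentage change can show only participants with a measured sum, and counting unmet criteria as failures over the FAS matches the ORR convention.

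**Conclusion.** The point holds as a minor flaw in a stated rule. As Sections 3.3.1 and 6.3 stand, a confirmed CR can be scored as not deep while a confirmed PR at 50% counts. Situation (a) is conditional on enrolling participants without target lesions, which the SAP alone does not settle. Situation (b) rests on the assumed nodal limits of 15 mm and 10 mm.

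The size is 1.6 percentage points per affected participant, with the number unknown and probably 0 to 2. Even two would be small against an interval about 25 points wide (28.1 to 53.6 in the illustration). No hypothesis test, decision rule or interim analysis uses the endpoint. The reason to act is that the error can only run downward, and the handling of these cases is better fixed before the data are seen.

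**What to change.** In Sections 3.3.1 and 6.3, define Deep Response as a confirmed CR, or a confirmed PR with at least a 50% reduction from baseline in the target-lesion sum. Reword the 0/1 coding and the not-deep rule in Section 3.3.1 to match, so that a confirmed CR scores 1 whether or not a percentage can be computed. Keep the FAS denominator. Naming baseline as the reference also fills a gap, since Section 3.3.1 does not say what the reduction is measured from.

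The cost is a small wording change in two sections and a small programming change. The downside is that a CR without a measured sum then counts as deep with no percentage behind it; a footnote giving the number of such participants would make that visible.

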3.4. Baseline Variables

3.4.1. Study drug, study treatment and baseline definitions

In this study, ‘**study drug**’ refers to sasanlimab or encorafenib or binimetinib for Sub-Study A, sasanlimab or axitinib or SEA-TGT for Sub-Study B, and ‘**study treatment**’ (or ‘**treatment group**’) refers to:

- Phase 1b Sub-Study A Dose Level 0: sasanlimab 300mg + encorafenib 300mg + binimetinib 45mg
- Phase 1b Sub-Study A Dose Level 1: sasanlimab 300mg + encorafenib 450mg + binimetinib 45mg
- Phase 1b Sub-Study A Dose Level -1: (sasanlimab 300mg + encorafenib 300mg + binimetinib 30mg
- Phase 2 Sub-Study A: To be determined from Phase 1b
- Phase 1b Sub-Study B: sasanlimab **CCI** + axitinib 5 mg BID
- Phase 1b Sub-Study B: sasanlimab **CCI** + axitinib 3 mg BID
- Phase 1b Sub-Study B: sasanlimab **CCI** + axitinib 5 mg BID + SEA- TGT DL0
- Phase 1b Sub-Study B: sasanlimab **CCI** + axitinib 5 mg BID + SEA- TGT DL1
- Phase 1b Sub-Study B: sasanlimab **CCI** + axitinib 5 mg BID + SEA- TGT DL-1

- Phase 1b Sub-Study B: sasanlimab **CCI** + axitinib 3 mg BID + SEA- TGT DL0
- Phase 1b Sub-Study B: sasanlimab **CCI** + axitinib 3 mg BID + SEA- TGT DL1
- Phase 1b Sub-Study B: sasanlimab **CCI** + axitinib 3 mg BID + SEA- TGT DL-1
- Phase 2 Sub-Study B: To be determined from Phase 1b

Phase 2 Sub-Study B participants will be assigned in the following 3 study arms:

- Arm B1: Participants who report (i) no prior advanced or metastatic therapy and (ii) locally assessed PD-L1 TPS \geq 50%
- Arm B2: Participants who report (i) no prior advanced or metastatic therapy and (ii) locally assessed PD-L1 TPS \geq 1% and TPS $<$ 50%
- Arm B2: Participants who report (i) prior advanced or metastatic therapy and (ii) locally assessed PD-L1 TPS \geq 1%

Start and end dates of study treatment:

The date/time of first dose of study treatment in a combination group is the earliest date/time of the first non-zero dose date/time for the study drugs in the combination.

The date/time of last dose of study treatment in a combination group is the latest date/time of the last non-zero dose date/time for the study drugs in the combination.

Definition of baseline:

Definition of baseline for efficacy and PRO analyses and for safety analyses

The last available assessment prior to the start of study treatment is defined as ‘baseline’ value or ‘baseline’ assessment for safety and efficacy analyses. If an assessment is planned to be performed prior to the first dose of study treatment in the protocol and the assessment is performed on the same day as the first dose of study treatment, it will be assumed that it was performed prior to study treatment administration, if assessment time point is not collected or is missing. If assessment time points are collected, the observed time point will be used to determine pre-dose on study day 1 for baseline calculation. Unscheduled assessments will be used in the determination of baseline. However, if time is missing, an unscheduled assessment on study day 1 will be considered to have been obtained after study treatment administration.

Participants who start treatment and discontinue from the study on the same day may have two different sets of data collected on study day 1 (one during study and one in the End of Treatment (EOT) visit). Data reported at the EOT visit are not eligible for baseline selection.

If a scheduled pre-dose measurement actually occurred post-dose, then the corresponding measurement will be treated and analyzed similar to an unscheduled post-dose measurement.

Baseline for RR and QT/QTc interval assessments will be derived from the visit where both RR and QT are not missing. Triplicate ECGs are collected in the study and the baseline for each ECG measurement is the average of the pre-dose replicate measurements on the baseline day. Unscheduled assessments will not be included in the calculation of the average. QTcB and QTcF will be derived based on RR and QT. The average of the replicate measurements will be determined after the derivation of the individual parameter at each time point.

Definition of baseline for immunogenicity analyses

The last available assessment prior to the start of treatment with sasanlimab is defined as 'baseline' result or 'baseline' assessment. If an assessment is planned to be performed prior to the first dose of sasanlimab in the protocol and the assessment is performed on the same day as the first dose of sasanlimab, it will be assumed that it was performed prior to sasanlimab administration, if assessment time point is not collected or is missing.

Definition of baseline for biomarker analyses

The last assessment prior to first dose of study treatment will serve as the baseline assessment for biomarker analyses. For biomarkers that are planned to be assessed on Cycle 1 Day 1, it will be assumed that the assessment was performed prior to study treatment administration, if the assessment time point is not collected or is missing.

